12.5 Interim Monitoring Plan

The study will be monitored using standard procedures and processes by an independent Data and Safety Monitoring Board (DSMB) of the Dana-Farber Harvard Cancer Center (DF/HCC).

Monitoring of key safety endpoints (relapse, grade 3 or higher treatment related toxicity, grade III-IV acute GVHD after study enrollment) will be conducted in accordance with the DF/HCC DSMB meeting. Since a concern for excess relapse exists, even though our preliminary studies do not support this, we will compare the relapse rate along with other key safety endpoints between two arms at each interim analysis. If, at any interim analysis, this difference is significant at the two-sided level of 0.05, this would trigger a consultation with the DF/HCC DSMB for additional review of early stopping. However, this will not be a formal stopping rule that would mandate automatic closure of study enrollment.

Interim analyses for efficacy will be performed every six months in conjunction with semi-annual DF/HCC DSMB meeting, beginning at the 25% information time, which is anticipated to occur approximately 1.5 years after the start of the trial. The interim results will be reported to the DF/HCC DSMB. However, these interim analyses will not have an effect in terms of stopping accrual to the study and terminate the study early in favor of alternative (superiority) or null hypothesis (futility). This is because i) due to a small sample size at the first interim analysis, stopping early for futility would result in substantially wide confidence intervals, larger Type II error, and thus leading to greater uncertainty about the magnitude of the steroid requiring cGVHD difference, ii) by the time of the second interim analysis, the study is anticipated to complete accrual, iii) even if the steroid requiring cGVHD difference is not as large as targeted, investigators are interested in learning the magnitude of the difference for further investigation, iv) stopping early for superiority would provide less safety data than planned and potential difficulty with the efficacy analysis and its interpretation.

12.6 Analysis of Primary Endpoints

The primary endpoint of this phase II trial is one year corticosteroid-requiring cGVHD rate.

The primary analysis will be a modified intent-to-treat analysis (mITT) fo with all randomized patients who receive any amount of the study drug, either obinutuzumab or placebo. Patients who are randomized but do not receive the study drug and off the study will not be included in mITT and be replaced (Section 5.11). The primary analysis will be performed using i) a Chi-square test for comparison of crude proportions, ii) comparison of cumulative incidence rates of corticosteroid-requiring cGVHD in the context of competing risks framework. In this analysis, death or relapse without developing a corticosteroid-requiring cGVHD will be considered as a competing event and cumulative incidence of death or relapse without developing cGVHD will also be reported, iii) multivariable competing risks regression analysis using the Fine and Gray model²⁵.

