12.2 Sample Size, Accrual Rate and Study Duration

The sample size is 200 eligible patients, based on event rates from DFCI 05-377. In this study, 65 patients who received rituximab as cGVHD prophylaxis were compared to a contemporaneous control group and the 1-year corticosteroid-requiring cGVHD rate was 21% in the rituximab group and 38% in the control group. Based on this information, we assume that the 1-year corticosteroid-requiring cGVHD rate will be 38% in the control group and hypothesize that there will be at least a 45% reduction in the obinutuzumab group to a 1-year corticosteroid-requiring cGVHD rate of 21%. With 200 eligible patients, the study will have 80% power to detect a 45% reduction in the obinutuzumab arm using a two-sided test at a significance level of 0.1. This power calculation is based on Fisher's exact test.

Accrual from 3 participating clinical sites (DFCI, MGH, Stanford) is projected to be approximately 100 patients/year, given competing trials and relapse or death prior to 3 months from HCT. Based on this projection, we anticipate that the study will complete its accrual in 2 years.

Patients who initially join the study but are later deemed ineligible due to exclusion criteria 3.2.6 will not be counted toward the overall accrual goal.

All surviving patients will be followed at least for 1 year after HCT for the evaluation of the primary endpoint

Special attention will be paid to the recruitment of women and minorites per NIH guidelines.

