12.3 Randomization and Stratification Factors

Randomization will be 1:1, stratified by center, conditioning intensity (myeloablative vs. reduced intensity) and donor type (matched related vs. matched unrelated) using permuted block algorithm within strata.

QACT will notify the research pharmacy of the randomization status of the patient by fax and via email ([contact]). The remainder of the study team will be blinded to which arm the patient will receive.

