12.7 Analysis of Secondary Endpoints

Secondary objectives include to determine the overall cGVHD rate after HCT, NIH moderate-severe cGVHD rate after HCT, cumulative incidence of non-relapse mortality and relapse, adverse hematologic events and infections, immunosuppression-free survival (IFS) at 1 and 2 years from transplantation, progression-free and overall survival at 1 and 2 years from transplantation, and immunologic correlates of B cell depletion.

For the comparison of GVHD, NRM and relapse, competing risks data analysis will be performed using Gray test²⁶ and Fine and Gray competing risks regression analysis²⁵. For PFS, OS, and IFS, standard survival analysis will be performed. Adverse hematologic events will be compared by cumulative incidence measures. All analysis will be repeated by disease group (myeloid vs. lymphoid).

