12.8 Analysis of Correlative Studies

The primary analysis for the correlative studies is concerns male recipients with female donors $(F \rightarrow M)$ and H-Y minor histocompatibility antigens (mHA). The analysis will be exploratory without adjustment for multiple testing. Based on the recent report from the [name] lab27, we hypothesize that patients with multiple anti-H-Y antibodies (defined as >=2 antibodies out of 6) at study entry are more likely to develop corticosteroid-requiring cGVHD at one year after HCT. Assuming 50 patients (from both arms) will undergo F→M HCT, if the one-year corticosteroid-requiring cGVHD rate is 55% and 15% for patients with and without multiple anti-H-Y antibodies, respectively, there will be 84% power to detect this difference. This power calculation is based on Fisher's exact test at the two-sided significance level of 0.1 assuming 18 patients in $F \rightarrow M$ 27 will have multiple anti-H-Y antibodies at the study entry. Using the H-Y protein arrays developed in the [name] lab, we measured IgG antibodies specific for DBY (one of HY mHA proteins) in 13 F→M who received rituximab prophylaxis (DFCI#05-377) and 10 F→M who did not receive rituximab. After 6 months post HCT, no one in the rituximab group developed anti-DBY reactivity whereas 4 out of 10 in the control group developed the anti-DBY reactivity (p=0.02). Extrapolating this result to this randomized phase II trial, if the anti-DBY response rates are 5% and 40% in the obinutuzumab and placebo group, respectively, in F \rightarrow M, there will be 88% power to detect this difference (Table). This power calculation is based on Fisher's exact test at the two-sided significance level of 0.1 assuming 25 patients will undergo F

M HCT in each treatment group.

Table. Power for various levels of responses between obinutuzumab and placebo arm

anti-DBY reactivity	(10%, 35%)	(5%, 35%)	(5%, 40%)
Power	57%	79%	88%

When data are available, we will repeat a similar analysis for multiple antibodies and investigate whether a combination of antibody responses is more discriminatory. We will also investigate whether H-Y antibodies measured prior to the initial administration of treatment are predictive of eventual cGVHD using ROC (receiver operating characteristic) curve analysis and multivariable regression analysis after adjusting for treatment arm. In addition, an appropriate statistical analysis will be applied for routine

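### Section 12.6 gives three analyses equal standing as the primary analysis at one two-sided 0.1 level, with no rule for which decides and no stated use of the randomisation factors

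*Combined protocol and SAP*

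**What the plan says.** The primary endpoint is a rate at one year from HCT (Sections 1.2, 12.1 and 12.6). Section 12.6 then states: "The primary analysis will be performed using i) a Chi-square test for comparison of crude proportions, ii) comparison of cumulative incidence rates". Death or relapse is the competing event in (ii). The third item is "multivariable competing risks regression analysis using the Fine and Gray model". All three stand under one sentence with the same status. The section gives no order of precedence, no split of the level and no rule for results that disagree.

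Section 12.2 sets the level once, "using a two-sided test at a significance level of 0.1", and adds: "This power calculation is based on Fisher's exact test". It also provides that "All surviving patients will be followed at least for 1 year after HCT for the evaluation of the primary endpoint".

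Three details have to be looked for elsewhere:

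- **The test for (ii).** Section 12.6 names none. Section 12.7, on secondary endpoints, says that for GVHD, NRM and relapse "competing risks data analysis will be performed using Gray test".
- **Multiplicity.** The only statement is in 12.8, on the correlative studies: "The analysis will be exploratory without adjustment for multiple testing".
- **Strata.** Sections 5.2 and 12.3 stratify randomisation by centre, conditioning intensity and donor type. Section 12.6 does not mention these factors.

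**The concern.** A trial with one significance level needs one test to spend it on. Here three correlated tests of the same treatment effect are each called primary, and (ii) and (iii) are not fully specified. If they disagree, the plan does not say whether the trial met its objective, and the result to lead with could be chosen after the data are seen. At stake are a modest excess of false positives over 10%, a small share of trials with no defined verdict, and a power statement in 12.2 for a test that 12.6 does not list. The randomisation factors are a lesser matter: leaving them out of the deciding test does not inflate error, but it can make that test slightly conservative.

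**Working it through.** **Inputs from the documents.** 200 patients, 1:1, so 100 per arm; 38% vs 21%; two-sided 0.1; planned power 80% (12.2). Interim efficacy looks cannot stop the trial (12.5), so they spend none of the level.

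**1. The plan's own figure.** Enumerating all 2x2 tables with 100 per arm, Fisher's exact test at two-sided 0.1 has 80.8% power. The stated 80% is reproduced. As a check by formula, the uncorrected sample size per arm is

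n = [1.645·√(2·0.295·0.705) + 0.8416·√(0.38·0.62 + 0.21·0.79)]² / 0.17² = (1.0608 + 0.5333)² / 0.0289 = 88.

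The continuity-corrected version is 100 per arm, which is the plan's 200.

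**2. The same design under the candidate tests of the one-year table (exact enumeration).**

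| Test | Power, 38% vs 21% | Size at common rate 29.5% / 38% |
|---|---|---|
| Fisher exact | 80.8% | 7.4% / 7.1% |
| Chi-square, uncorrected | 84.8% | 10.3% / 9.7% |
| Chi-square, continuity-corrected | 80.6% | 7.3% / 7.1% |

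The correction can change the verdict. With 38 vs 27 events per 100, the uncorrected statistic is 200·(38·73 − 27·62)² / (100·100·65·135) = 200·1100² / 87,750,000 = 2.758, p = 0.097. With the correction it is 200·1000² / 87,750,000 = 2.279, p = 0.131, the same as Fisher's p to three decimals. Section 12.6 does not say whether the correction applies.

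**3. Any one of the three counts as success.** This needs simulation. All analyses stop at 12 months and follow-up is complete. Patients with a competing event then stay in the Fine-Gray risk set to 12 months, so the Gray and Fine-Gray tests reduce to log-rank and Cox tests on subdistribution times. Fine-Gray includes the three randomisation factors.

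Assumed: permuted blocks of 4; centre shares 55/30/15% (the 15% from Appendix D, 15 of about 100 patients a year); conditioning split 50/50. The related-donor share comes from the pilot: 31 = 23p + 38(1 − p), p = 0.467. The pilot-sized donor effect is ln(0.77)/ln(0.62) = 0.547, from the two-year figures in 2.1, so it is only suggestive.

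- Single-test size with no or pilot-sized strata effects: chi-square 9.7-9.9%, Gray 9.5-10.0%, Fine-Gray 9.9-10.4%.
- Any-of-three at 29.5% / 38%: 11.0 / 11.6% with no strata effect, 11.2 / 12.0% with the pilot-sized effect (20,000 trials each, Monte Carlo error about 0.2 points).
- A second simulation with different assumptions (donor effect ±25% around the mean, two-level centre factor) gave 11.4-11.8%.
- Verdicts not unanimous: about 2-4% of trials with no or pilot-sized effects. Rates up to about 6% appear only under strong effects that are pure assumption.

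**4. Other ways to read three tests.** If all three must succeed, power is about 83-85% and size cannot exceed that of the smallest single test. If the level were split (0.1/3 = 0.0333 each), power would fall to 70.3% for the chi-square and 65.0% for Fisher.

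**5. Strata.** Crude chi-square against an uncorrected Cochran-Mantel-Haenszel (CMH) test on four donor-by-conditioning strata:

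| Strata effect | Size, crude vs CMH | Power, crude vs CMH |
|---|---|---|
| None | – | 84.9% vs 84.7% |
| Pilot-sized | 9.7-9.8% vs 10.0-10.3% | 85.5% vs 85.7% |
| Strong (assumed) | 7.9% vs 9.5-10.0% | 86.4% vs 88.0% |

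Using all 12 strata changes CMH power little: 84.4%, 85.6% and 88.4% in the same order.

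**The case against.** The best defence is that the intended lead test can be inferred. The endpoint is a one-year rate, the sample size compares two one-year proportions, and the first analysis listed tests those proportions. With complete follow-up the 12-month cumulative incidence equals the crude proportion, so (i) and (ii) can be nearly the same comparison. The text can also be read as requiring all three, which costs no planned power. This is fair, and it limits the harm. But it is an inference: the sentence gives the three equal standing, and neither reading is written down.

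A reader might also infer that Fisher's exact test is a rival primary test carrying the 0.1 level. The documents do not support that. Section 12.2 names Fisher only as the basis of the power calculation, and the contrast with the chi-square disappears once a continuity correction is applied. What stands is narrower: the power is stated for a test other than the one in 12.6, and the correction is unspecified.

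On strata, calling the proportions crude does settle (i) as unadjusted. The open question is (ii) and (iii), and whether an unadjusted deciding test is wanted. The loss from it is small.

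**Conclusion.** The point holds and should be fixed, though it does not threaten the design. With any-of-three allowed, the one-year false-positive rate is about 11-12% instead of 10%, and about 2-4% of trials end with split verdicts. These figures rest on complete follow-up, a 12-month horizon, the three randomisation factors as the Fine-Gray covariates, the assumed block size and shares, and no or pilot-sized strata effects.

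Three stronger readings are tempting and not supported:

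- **Three tests at 0.1 give 1 − 0.9³ = 27.1%.** That assumes independence; these tests share the same patients and events and are highly correlated.
- **Because (ii) and (iii) state no horizon and follow-up runs to two years (5.10), the curves might be compared over two years.** Simulation of that reading gave 14.4-14.5%. The endpoint is defined at one year throughout, so I do not rely on it, but it is a reason to write the horizon down.
- **A free choice of covariates in (iii) could push the error higher still.** The documents name no covariates, so any such figure rests on invented effects.

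Leaving the strata out of the deciding test does not inflate error. It costs roughly 0 to 2 points of power.

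**What to change.** In 12.6, before unblinding:

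- Name one deciding test of the one-year proportions at two-sided 0.1, and state whether a continuity correction is used. A CMH test without correction, stratified by randomisation factors, is preferable: its power change against the crude chi-square is about 0 to +2 points and its size stays closer to 10%. The uncorrected chi-square alone is an acceptable simpler choice.
- If CMH is chosen, fix the strata now: either all three factors, or donor type by conditioning intensity with the omission of centre stated. Use the donor category recorded at randomisation. This matters for 7/8-matched donors, whom 3.1.4 admits but whom 12.3's two donor labels do not cover.
- Report the risk difference with a 90% interval. At 38% vs 21% the half-width is about 1.645·√(0.2356/100 + 0.1659/100) = 0.104, or 10 points.
- Label (ii), as a Gray test, and (iii), with treatment, centre, conditioning intensity and donor type as covariates, as supportive. Restrict both to 12 months from HCT.

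In 12.2, restate the power for the named test.

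The cost is wording in two sections and a few lines of code, with no extra patients or visits; N stays at 200. The sponsor gives up only the choice among three primary results. Keeping three co-equal tests with a split level would be the expensive route.

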5.2 Trial Screening and Entry

Subjects deemed potentially eligible by their treating physicians will be screened for enrollment after day +60 from transplantation. Once screened, deemed eligible and registered, the subject will be randomized in a 1:1 to the active treatment (obinutuzumab) or placebo arm. Stratification will be by center, conditioning intensity and donor type, using a permuted block algorithm within strata. Blinding will be maintained at the level of the Research Pharmacy.

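### Randomization is stratified, but no primary or secondary analysis is stated to use the strata; using them is a small, wording-only gain and validity is not at risk

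*Combined protocol and SAP*

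**What the plan says.** Section 5.2 of the protocol reads "Stratification will be by center, conditioning intensity and donor type, using a permuted block algorithm within strata". Section 12.3 repeats this and gives the levels: "stratified by center, conditioning intensity (myeloablative vs. reduced intensity) and donor type (matched related vs. matched unrelated". With the three sites of section 12.2 that makes 3 x 2 x 2 = 12 strata.

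Section 12.6 lists three primary analyses:
- item (i) is "The primary analysis will be performed using i) a Chi-square test for comparison of crude proportions";
- item (ii), which names no test, is given as "comparison of cumulative incidence rates of corticosteroid-requiring cGVHD in the context of competing risks framework";
- item (iii), which names no covariates, is given as "multivariable competing risks regression analysis using the Fine and Gray model".

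For GVHD, non-relapse mortality and relapse, section 12.7 says "competing risks data analysis will be performed using Gray test", together with Fine and Gray regression. For the survival endpoints it refers only to standard methods. The one split it plans is by disease group, which is not a randomization factor.

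Section 12.2 states "With 200 eligible patients, the study will have 80% power to detect a 45% reduction in the obinutuzumab arm", for 38% versus 21% at two-sided 0.1, computed for Fisher's exact test without strata.

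**The concern.** Stratified randomization balances the arms on the stratifying factors. If those factors predict the outcome, the difference between arms varies less from trial to trial than an unstratified test assumes. The unstratified test is then conservative and gives up some power. A test that uses the strata recovers this.

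A second, smaller matter is prespecification. Item (ii) has no named test and the models in (iii) and 12.7 have no named covariates, so whether the randomization factors are used is left open. The accurate statement is that their use is not stated, not that it is ruled out.

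At stake is efficiency. Type I error is not inflated.

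**Working it through.** **1. The plan's own figure.** Inputs from 12.2: 100 per arm, 38% versus 21%, two-sided 0.10. Enumerating all pairs of binomial outcomes gives:

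| Test | Exact power |
|---|---|
| Fisher | 80.8% |
| Chi-square, uncorrected | 84.8% |
| Chi-square, continuity-corrected | 80.6% |

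The stated 80% is reproduced with Fisher's test. The chi-square of 12.6 meets it with or without correction.

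**2. How prognostic are the strata?** The documents inform only donor type. Section 2.1 gives 2-year corticosteroid-requiring cGVHD in the earlier rituximab trial (the trial in which "65 patients who received rituximab as cGVHD prophylaxis were compared to a contemporaneous control group") as 23% with related and 38% with unrelated donors, 31% overall. The corresponding figures for any cGVHD are 35%, 59% and 48%. Reading these as simple fractions of 65 and searching splits with 10 to 55 related donors, only 31 related and 34 unrelated reproduces all six:
- corticosteroid-requiring: 7/31 = 22.6%, 13/34 = 38.2%, 20/65 = 30.8%;
- any cGVHD: 11/31 = 35.5%, 20/34 = 58.8%, 31/65 = 47.7%.

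Odds ratio = (13/21)/(7/24) = 2.12. SE of the log = sqrt(1/13 + 1/21 + 1/7 + 1/24) = 0.556, so the 95% interval is 0.71 to 6.3. Fisher p = 0.19. A donor effect is plausible but not shown.

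**3. Crude versus stratified test.** In each stratum with n patients (nc control, nt treated), m events and xc control events, E = nc·m/n and V = nc·nt·m(n − m)/(n²(n − 1)). The CMH statistic is Z = Σ(xc − E)/√ΣV, and the test rejects when |Z| ≥ 1.645. No continuity correction is used in either test.

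The simulation used 400,000 trials per scenario (Monte Carlo SE of size about 0.0005), 200 patients, and marginal rates of 38% and 21%. Size was evaluated at common rates of 29.5% and 38%. Assumptions not in the documents:
- permuted blocks of 4;
- conditioning split 50/50;
- center shares 55/30/15% (the 15% follows from 15 per year in Appendix D 5.3 against 100 per year in 12.2);
- all conditioning and center effects.

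The unrelated share is 34/65. CMH-4 uses conditioning x donor type; CMH-12 adds center.

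| Odds ratios | Size at 29.5%, crude / CMH-4 | Size at 38%, crude / CMH-4 | Power %, crude / CMH-4 / CMH-12 |
|---|---|---|---|
| None prognostic | .101 / .100 | .101 / .101 | 84.7 / 84.5 / 84.4 |
| Donor 2.12 | .096 / .099 | .095 / .099 | 85.0 / 85.3 / 85.2 |
| Donor 3 | .092 / .100 | .090 / .100 | 85.2 / 86.2 / 86.0 |
| Donor 6.3 | .078 / .099 | .074 / .100 | 86.3 / 88.8 / 88.7 |
| Moderate: donor 2.12, conditioning 1.5, centers 1/1.5/0.75 | .094 / .098 | .092 / .098 | 85.3 / 85.7 / 85.9 |
| Strong: donor 3, conditioning 3, centers 1/2/0.5 | .079 / .094 | .077 / .093 | 86.4 / 88.1 / 88.6 |

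At donor odds ratio 2.12 the 90% interval for the risk difference narrows from 20.7 to 20.5 points, with coverage 90.1% (crude) and 89.7% (stratified). Blocks of 6 give power of 85.1% and 85.4%.

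**4. Sensitivity to the assumed shares.** A second simulation (200,000 trials per scenario) used center shares 60/25/15%, donors 35/65 related/unrelated, and the odds ratio taken directly from 23% and 38%: (0.38/0.62)/(0.23/0.77) = 2.05. Power was 85.0% crude versus 85.1% over 12 strata, or 85.3% stratifying by donor type alone. With very strong effects (control rates from 3% to 81% across strata) it was 86.9% versus 90.2%, and crude size fell to 0.068.

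**5. Continuity correction.** At donor odds ratio 2.12, corrected power is 80.7% crude and 81.3% for CMH-4, about 4 points below the uncorrected tests. This outweighs the effect of the strata, and 12.6 does not say which form applies.

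**The case against.** The strongest reply is that nothing of consequence follows. At the only prognostic effect the documents suggest, the gain is 0.3 points, worth about one patient per arm: exact chi-square power is 84.8% with 100 per arm, 85.0% with 101 and 85.4% with 102. The planned test is valid and already exceeds 80%. The 2-point gains need either the upper limit of a wide interval from 65 patients or conditioning and center effects that no section supports. The multivariable models may already contain the factors, so one sentence naming covariates could be enough. The stratified option also leaves center out, and under strong effects its size stays at 0.093 to 0.094.

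Most of this is right, and it fixes the weight of the point: modest. It does not remove it. The price is about 0.2 points in the worst case shown, and the change also settles choices that 12.6 leaves open. Center is left out because of sparse cells; at donor odds ratio 2.12 this loses nothing (85.3% against 85.2% with 12 strata).

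Two objections to scope stand. No benefit was computed for the stratified Gray test or the adjusted regressions; those follow for consistency. Rewording donor type in 12.3 touches the definition of a randomization factor, so it must match how patients were actually allocated.

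**Conclusion.** The point holds as an efficiency and prespecification matter. Neither 12.6 nor 12.7 states that the randomization strata are used, and the first-listed primary test ignores them. The crude test is valid and at most mildly conservative.

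At the donor effect suggested by section 2.1, using four strata adds about 0.3 points of power and brings size from 0.095–0.096 to 0.099. The gain is about 2 points under strong assumed effects, and about 0.2 points are lost if no factor is prognostic.

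These sizes rest on the assumed block size, center and conditioning shares, and effects of conditioning and center. They also carry a donor effect over from 2-year cumulative incidences in rituximab-treated patients, treated as simple fractions, to a 1-year endpoint. The textual gap depends on none of this. The change should be made, but the trial does not stand or fall by it.

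**What to change.** - **12.6(i):** replace the crude test with a CMH test, without continuity correction, over conditioning intensity x donor type (4 strata). Report a Mantel-Haenszel risk difference with a 90% interval. Keep the crude chi-square, also uncorrected, as supportive and not as a further primary test.
- **12.6(ii) and 12.7:** specify a Gray test stratified by the same 4 strata.
- **12.6(iii) and 12.7:** enter all three randomization factors as covariates in the Fine and Gray models. Center enters here and not in the strata.
- **12.7, survival endpoints:** say in the same sentence whether the factors are used for PFS, OS and IFS. The figures above do not bear on these.
- **12.3:** clarify donor type as related versus unrelated. Section 3.1.4 admits 7/8 donors, who have no level under the present labels. First confirm that this agrees with how such patients are allocated, so that analysis and randomization strata do not diverge.

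Twelve strata would be sparse: the center expected to give 15 patients per year contributes about 15 x 2 = 30 over two years, or 30/4 = 7 to 8 per conditioning-by-donor cell if evenly split.

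The cost is wording in 12.3, 12.6 and 12.7. Sample size does not change, and neither does conduct, provided the 12.3 wording matches current allocation. The statistical price is about 0.2 points of power if no factor is prognostic.
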